Specific Aim 1 - Ferumoxytol (Fe) MRI

We will pursue two approaches for the detection of ferumoxytol signal: R2* and QSM.

Specific Aim 2 - MR Perfusion and Oxygenation

We will test several approaches for MR perfusion measurements without a contrast agent as well as BOLD imaging for probing placental oxygenation.

RESEARCH DESIGN AND METHODS OVERVIEW

Patients can be diagnosed with FGR anytime between 27 0/7 - 32 6/7 weeks gestation. All patients will be offered participation into the study at the time of FGR diagnosis.

Research Procedure Descriptions

Blood/urine collection for research

Blood and urine samples are collected at the consenting visit and at the time of delivery. A total of 10 mL of blood is collected via venipuncture along with an aliquot of a urine sample. For research visits that coincide with clinical visits, research blood samples are collected in conjunction with clinical samples, saving subjects an additional needle stick. All subjects are asked if they wish to have left over research samples banked for future unspecified research. Blood and urine samples will be analyzed to monitor relevant maternal growth factors, multiplex assays for Cytokine panel and MMPs. Urine will be tested for Shed VECad.

60 minute MRI:

This MRI scan will take approximately 60 minutes. Prior to entering the MR suite, subjects are screened again for MRI safety and compatibility. The MR imaging exam is expected to take approximately 60 minutes with some additional time to get subjects comfortably placed in the scanner. Subjects are made as comfortable as possible in the bore and are provided with an alarm, which allows them to get the attention of the MR technologist conducting the scan. There is a break between scans to ensure the comfort of the subjects.

Ferumoxytol administration:

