The patient's clinical provider will be informed that the patient is participating in the FGR study and that, if any unknown conditions or illnesses are identified during the course of prenatal care, we would appreciate knowing from them with patient's consent. We also set up a mechanism in the obstetrics triage unit in the UnityPoint Health-Meriter inpatient facility for all pregnant women admissions to include a specific alert for the nursing staff that the patient is a study participant and that patients should be informed, and, with the patient's permission, study coordinator can be notified for any new conditions and/or illnesses.

SUBJECT POPULATION AND ELIGIBILITY CRITERIA

Sample Size

The total sample size is 20.

Inclusion Criteria

1. Pregravid BMI 18.5-39.9 Kg/m²
2. Women with singleton pregnancies
3. Ultrasound confirmed pregnancy dating prior to 14 weeks gestation
4. Gestational age of 27 0/7 - 32 6/7 weeks at FGR diagnosis based on standard clinical criteria.
 - a. Estimated Fetal Weight: less than 10 percentile OR
 - b. abdominal circumference less than 10th percentile

Exclusion Criteria

1. Diagnosis of preeclampsia at FGR diagnosis
2. Gestational Diabetes Mellitus or type I/II Diabetes Mellitus
3. Known fetal chromosome abnormality, structural malformation or syndromes in current pregnancy
4. Known fetal viral infection syndrome
5. Alcohol/drug/tobacco use in current pregnancy
6. History of sickle cell anemia, sickle cell trait or other inherited anemia with risk of iron overload
7. Contraindications to MRI (such as claustrophobia, metallic implant, etc.) based on MRI Screening

8. Participation in other interventional clinical trials, including those with other investigational agents not included in this trial, within 30 days of the start of this trial and throughout the duration of this trial
9. Any physical or psychological symptom, based on the clinical judgment of the study physician that would make a participant unsuitable for the study.

Final subject eligibility will be determined by the Principal Investigator or Sub-Investigator delegated the corresponding task.

SUBJECT IDENTIFICATION AND RECRUITMENT

Identification in clinical practice: Investigators own practice

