obtained. Potential subjects will be encouraged to take as much time as needed to consider participation.

An informed consent for participation in the study is obtained from each eligible patient, including a consent for Fe-MRI. Patients of all ethnicities for both groups are eligible.

Screening for Eligibility

1. A subject would fill out a permission to contact form in their respective clinic and the research coordinator would call the patient.
2. The telephone script would be used to determine baseline eligibility. The coordinator may send the subject a consent form so they have time to review before the consenting visit. The phone script will also ask patients if they would allow the coordinator to review their medical records before scheduling a consenting visit.
3. A consenting visit would be set up at the Center for Perinatal Care so that the subject could meet with the coordinator to ask questions and sign the informed consent document.
4. The inclusion/exclusion criteria will be reviewed with the patient.
5. Once the patient has signed the consent form documents, she will be given a copy for her records.
6. The sensitive information will be collected by the review of medical records. General information that we can rely on the patient will be collected by oral interview, however rigorous review of medical records would be necessary before enrolling the subject into the study. Per protocol, Exclusion criteria: if a patient is using tobacco/alcohol/drugs they would be excluded from the study since these factors could alter the outcome of their pregnancy putting these patients at higher risk. A MRI screening compatibility form will be completed to make sure it is safe for the patient to have an MRI performed. This is a standard form used by UW for all imaging procedures.

Enrollment

A research subject will be defined as “enrolled” in the study when they meet the following criteria:

- The subject has been consented by study staff.
- The subject and study staff have completed all screening documentation.
- The PI has verified that the subject meets all of the inclusion criteria.
- The PI has verified that subject meets none of the exclusion criteria.
- The subject has been assigned to the protocol by study staff.
- The subject has scheduled a study visit.
- The subject has received the study intervention.

On Study/Follow-up Visits

All procedures are described in detail in the “Research Procedure Descriptions” section of the protocol.

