Patient with preeclampsia and /or fetal growth restriction are at increased risk of preterm delivery, cerebral palsy and fetal/neonatal death. There are many perinatal implications of preterm delivery including common complications like respiratory distress syndrome, intraventricular hemorrhage, patent ductus arteriosus, necrotizing enterocolitis and bronchopulmonary dysplasia with long-term need for oxygen.

Allergic/anaphylactic reaction

Regarding the possibility of an allergic/anaphylactic reaction and its impact on the pregnancy and fetus, the impact would not be severe, based on data on allergic reaction from AMAG Corporation, University of Arizona and Georgetown University School of Medicine, described below. Ferumoxytol has been used clinically in pregnant women at Meriter.

All intravenous iron infusions have some serious risks including anaphylactic reactions and death. However, critical review of the literature shows that these events are rare and some of the events are due to physician interventions for treatment of minor allergic reactions. These events most frequently have been reported in older patients and individuals with underlying chronic conditions. We wish to emphasize that Ferumoxytol is one of the iron preparation with lowest rate of reactions. It is approved for use during pregnancy. We have provided extensive details in our IND application based on which we now have FDA approval to conduct this research as proposed.

All intravenous iron preparations have been described to have serious allergic reactions in a small number of subjects receiving such treatments. These serious adverse events for ferumoxytol include anaphylactic reactions. The agency is now requiring a boxed warning with new cautions and has asked AMAG Pharmaceuticals to add a new contraindication of a strong recommendation against use in patients who have had an allergic reaction to any intravenous (IV) iron-replacement product.

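### A contraindication the protocol itself reports (prior allergic reaction to any intravenous iron) is not among its eligibility criteria, and no described pre-dose step asks about it

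*Combined protocol and SAP*

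**What the plan says.** The Allergic/anaphylactic reaction section, under Potential Risks, states that intravenous iron carries serious risks, including anaphylaxis and death. It reports a required boxed warning and a request that the manufacturer add a "contraindication of a strong recommendation against use in patients who have had an allergic reaction to any intravenous (IV) iron-replacement product".

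The eligibility section lists 4 inclusion and 9 exclusion criteria. Three exclusions come nearest to this topic:

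- Exclusion 6: "History of sickle cell anemia, sickle cell trait or other inherited anemia with risk of iron overload".
- Exclusion 7: "Contraindications to MRI (such as claustrophobia, metallic implant, etc.) based on MRI Screening".
- Exclusion 9: "Any physical or psychological symptom, based on the clinical judgment of the study physician" that would make the woman unsuitable.

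The Enrollment section requires that "The PI has verified that subject meets none of the exclusion criteria". Screening for Eligibility says that "rigorous review of medical records would be necessary before enrolling the subject into the study". It also describes a safety form for the scanner: "A MRI screening compatibility form will be completed to make sure it is safe for the patient to have an MRI performed". The 60 minute MRI section adds a second scanner check: "Prior to entering the MR suite, subjects are screened again for MRI safety and compatibility".

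For the drug, Dosing and Administration and the Visit 1 description have the nurse record pulse, blood pressure and fetal heart rate and then start the infusion. The visit table also schedules a concomitant-medication review at Visit 1.

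**The concern.** The protocol reports a drug-specific contraindication in its risk section and does not carry it into the list that decides who is dosed. A woman who has reacted to another intravenous iron product meets every written criterion, provided she is otherwise eligible.

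The situation is foreseeable. The Inflammation section of the Background says that anemia is common in pregnancy and that physicians frequently use parenteral iron when oral iron fails, so some women approached may have had it before.

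The Visit 1 description says its procedures are for research purposes only, and both mother and fetus are exposed to any reaction. At stake is participant safety. No endpoint, sample size or error rate is affected.

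**Working it through.** The claim is mainly textual, and the plan has no figure of its own to reproduce.

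**Count of criteria.** Inclusion: body mass index, singleton pregnancy, early ultrasound dating, and gestational age at diagnosis of growth restriction (parts a and b counted as one item) = 4. Exclusion: 9. Total 4 + 9 = 13. Criteria naming allergy, hypersensitivity, prior intravenous iron or a contraindication to ferumoxytol: 0.

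**Do the nearest exclusions cover it?**

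- Exclusion 6 concerns iron overload, a different drug risk.
- Exclusion 7 uses the word contraindications, but for MRI only.
- Exclusion 9 turns on a symptom. A past drug reaction in a woman who is now well is a history, so reaching her through this item depends on a generous reading by the physician.

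**How other hazards in the same protocol are handled.**

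| Hazard | Named exclusion | Described pre-procedure check |
|---|---|---|
| MRI contraindication | Yes (7) | Screening form; re-screen before the scanner |
| Iron overload | Yes (6) | Commitment under Impact on the Fetus to select only women not at risk |
| Prior reaction to intravenous iron | None | None that names it |

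**When the allergy safeguards act.** Pre-notifying the anesthesiologist and monitoring every 5 to 15 minutes (Supportive Care; Dosing and Administration), stopping the infusion at signs of a reaction (Data and Safety Monitoring Plan), and the rule triggered by 2 anaphylactic reactions (Study Stopping Guidelines) prepare for, detect or manage a reaction. None screens a woman out before dosing.

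**Scale, for orientation only.** The documents give no prevalence p for this history. Assume p = 0.001 to 0.01.

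- Expected among 20 infused: 20p = 0.02 to 0.2.
- Chance of at least one among 20, if no discretionary check catches her: 1 − 0.999^20 = 0.0198 (2.0%) to 1 − 0.99^20 = 0.1821 (18.2%).
- Expected among 60 approached: 60p = 0.06 to 0.6.

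These are chances of dosing a woman with the history, not chances of anaphylaxis. The protocol's only reaction rate is 0.02% for anaphylaxis among ferumoxytol recipients in general. It gives 1 − 0.9998^20 = 0.0040, or about 0.4%, for at least one event in 20. It is not a rate for women with a prior reaction, who are the group the contraindication addresses.

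**The case against.** The best reply is that several ordinary steps stand between such a woman and the infusion. Medical history and concomitant medications are scheduled at screening, and the medication review is repeated at Visit 1. Records must be reviewed before enrollment. The investigator makes the final eligibility decision and can withdraw a woman who is no longer an appropriate candidate. Drug allergies would usually surface in such a review. The vial is said to carry warning information and the hospital pharmacy has its own ferumoxytol guidelines; either might state the contraindication. The telephone script, label, pharmacy guidelines, Manual of Procedures and IND are mentioned but not reproduced, and part of the supporting safety documentation was not available to read. The dose is also half the usual initial dose, given once under close observation, and the MRI form is standard imaging practice rather than evidence that drug allergy goes unchecked.

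Much of this is fair. The discretionary checks are real and may catch most cases, the prevalence range is an assumption without evidential weight, and no claim can be made about the unseen documents. What does not follow is that the protocol is adequate as written. None of the described steps is said to ask about a prior intravenous-iron reaction or to exclude on the answer. The eligibility list, screening steps and infusion procedure are all in the text, and an exclusion belongs in the list that the investigator verifies. The lower dose and close observation do not answer a contraindication based on history.

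**Conclusion.** The concern holds. 0 of 13 criteria and 0 described screening steps name a prior allergic reaction to intravenous iron, although the protocol reports it as a contraindication. Read as written, the criteria admit a woman who should not be infused.

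The number of women affected is unknown and probably small. The finding rests on the wording of the eligibility rule and not on the illustrative prevalence. It assumes only that the eligibility list shown is complete, and it makes no claim about the documents that are not reproduced. Because the infusion is research-only in pregnant women and the remedy is trivial, this should be corrected before any further woman is dosed.

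**What to change.** Add a tenth exclusion: *prior allergic or hypersensitivity reaction to ferumoxytol or any intravenous iron product*. Add a matching question to the Screening for Eligibility steps and confirm the answer in the record review already planned. The investigator's check against the exclusion list then covers it without further change.

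The cost is one line and one question, with no effect on sample size or analysis. Under the same illustrative range, 0.06 to 0.6 of the 60 women approached would be lost. A vague self-report could exclude a woman whose earlier event was not allergic; the record review limits that.

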This study at the University of Arizona (UA) (PI: [name]) is recruiting women with anemia in pregnancy greater than 20 weeks gestation for treatment with either oral iron or with feraheme. They are randomized in a 1:1 allocation. So far, 23 women have been recruited, 11 in the oral iron arm and 12 in the IV feraheme arm.

There have been no anaphylactic reactions and no concerns raised otherwise about the study. The study is too early in recruitment to determine outcomes such as a change in laboratory values or birth outcomes, but there has not been a concerning pattern emerging in any outcomes at this early stage.

Prior administration of Ferumoxytol at UPH-Meriter Hospital

The protocol at Unity Point Meriter was developed based on our research proposal and dose for clinical contrast-MRI at Meriter is same as in our research protocol. The following were the results from women administered ferumoxytol during pregnancy. UPH-Meriter was unable to provide us with pregnancy outcome data. Ferumoxytol is used as a contrast agent for pulmonary angiography in pregnancy patients who present with symptoms of pulmonary embolism. It is used during pregnancy for assessment of pulmonary vasculature.

The protocol was established in late 2017. All ferumoxytol is ordered by the ordering providers, administered on their respective floors, and monitored by their staff. The UPH-Meriter pharmacists have created guidelines regarding dosing, including reporting adverse reactions.

The UPH-Meriter pharmacy does standard weight-based dosing, based on the UW Health guidelines. The standard dose is 3 mg/kg with a maximum of 510 mg.

A search was done of UPH-Meriter pharmacy records for all administration of ferumoxytol for the past 15 months, between 12/04/2017 and 4/01/2019. This medication was administered 29 times to 27 pregnant patients and 2 non-pregnant patients. The two non-pregnant patients were men, who acute kidney injury.

Ultimately, PE was ruled out in all the women. Two patients required another imaging study (CTA in both cases) to provide further information. One patient ruled out for PE, but was found to have cholelithiasis.

[name], PhD, [name] and [name]. The MRI research team will analyze and interpret the findings of the MRI imaging to determine if macrophages are detected in the uterine wall. The study PI, [name], and [name] will make the final decision for interpretation of the MRI imaging.

The PI will provide appropriate counseling to the subject and their primary obstetrician, as he is a Maternal-Fetal Medicine (MFM) specialist who can explain the findings and to reduce the subjects' anxiety. [name] is a UW Ob/Gyn physician, working in the UPH-Meriter Perinatal Clinic who routinely reviews MRI scans and counsels patients with at-risk pregnancies. [name] is the most qualified physician-scientist in the region to explain to the subject the meaning of the findings and how she will be monitored.

The study PI will disclose results from the MRI scan to subjects. The primary finding will be the presence or absence of macrophages at the maternal-fetal interface at the site of implantation. If we observe other changes in the placenta, such as lack of perfusion in intervillous space, we will also report this finding. The PI will discuss these findings with the subject in layman's terms and describe the modifications in clinical care as a result of these findings.

Interpretation of clinical monitoring will be enhanced based on MRI findings.

We may confirm that there are no perfusion defects and no evidence of macrophage recruitment in the placental bed. This would be enormously reassuring to the subjects, particularly the absence of perfusion defects. However we will not suggest to the clinician to change the course of monitoring.

If we detect perfusion defects or recruitment of macrophages in the placental bed, we would suggest that these subjects have following modification in clinical care.

- a. If fetal growth is not already being monitored, we would recommend to the clinic that additional monitoring be added to clinical care.
- b. The number of visits for patients may be increased to monitor for development of new or acceleration of hypertension, indicative of pre-eclampsia.
- c. Depending on the severity of placental lesions, we may inform clinicians as to which patients may require earlier delivery.

In this context, these three modifications will empower clinicians to provide individualized care based on novel advanced and sophisticated imaging information.

Review of MRI by the MRI research team will occur within one week and an appointment for counseling for the subject would be scheduled within the following week. This timeline of counseling the subject within 2 weeks is safe given that a) the subject is already being monitored for the emergence of disease diagnosis and, b) we are detecting placental lesions that are premonition of emergence of severe fetal growth restriction or preeclampsia, which are not likely to occur until 4-8 weeks after the infusion MRI.

The PI, a physician at the Center for Perinatal Care clinic, will have a face to face research visit with the subject about their MRI findings. PI will also contact with the subject's physician to discuss the results. This will occur within two weeks of the last MRI scan.

Results from the MRIs will be made available in the subject's medical record.

Blood and urine samples collected for analysis will not provide clinical information, this is pioneering work and no clinical data exists for this kind of work.

DATA COLLECTION, HANDLING, AND RECORD KEEPING

Privacy/Confidentiality

The paper research records will be kept confidential. The results of this study may also be used for medical and scientific publications, but the subject will not be identified personally in any presentations or reports related to this research.

The information collected from subjects and from their medical records will be used by the researchers and research staff of the UW-Madison and its affiliates (the University of Wisconsin Hospital and Clinics and the University of Wisconsin Medical Foundation) for this study. It may also be shared with others at the UW-Madison.

Any paper documentation including the consent form will be kept in the UW Ob/Gyn clinical research office (located at McConnell Hall) and locked in a cabinet. The consent form will be stored in a separate file cabinet from the patient data. There is limited access to the office and only the study coordinators have a key to the locked files.

Patient information that is entered into the database stored on department servers will be coded; only the investigators involved in this study will have access to the research-related information. Results from this study may also be used for medical and scientific publications, but the subject will not be identified personally in any presentations or reports dealing with this research.

The information will be reported only to the study team, either by Epic note or direct contact. The deidentified data will travel to REDCap so no one other than the study team will have access to the information.

Results from MRI imaging (but not blood or urine test results) will be entered into patient's medical records.

Others at UW-Madison and its affiliates who may need to use the subject's health information in the course of this research:

- UW-Madison regulatory and research oversight boards and offices
- University of Wisconsin financial and accounting services
- Research support services staff at the UW-Madison and its affiliates

Others outside of UW-Madison and its affiliates who may receive the subject's health information, without any identifiable information, in the course of this research:

- National Institutes of Health
- US Food and Drug Administration

Data Collection

Research data collected is coded with a unique study identification number assigned to each subject upon enrollment. Confidentiality is protected by keeping paper research files in a secured office while unsupervised; all excess paper copies will be shredded; data is entered into the secure, password protected clinical trial management software, OnCore and the Research Electronic Data Capture (REDCap) system (refer to the Data Management section for more information); computer monitors have screensavers, login screens will be password protected; workstations are password protected; and firewall security protection is in place.

MRI data will be stored on the UW Department of Radiology PACS (Picture Archiving and Communication System). All workstations used to access and process images are password protected to ensure confidentiality. The MR systems are connected to the network within the hospital firewall, and images and unprocessed image data will be transferred to password-protected computers in the Departments of Radiology and/or Medical Physics.

For all research data sent to PACS, a unique study/subject code is used to identify the imaging data. The unique study number includes the prefix "RMR" allowing it to be identified by a filter on the PACS system as a research scan to be kept separate from any clinical data. This strategy is another measure used to prevent research data from inadvertently being entered into medical records.

Study subjects are asked to provide consent to have left over research samples banked for future unspecified research. Study data as well as specimens are retained for future use. It is not known what these specimens will be used for. Samples and data will be anonymized, with all identifiers removed, including all study codes. The specimens are stored at Meriter hospital in the 7th floor lab of [name]. This restricted area requires a specified badge for access, only the researchers who work in this lab have access.

- All clinical imaging and biochemical data obtained from this study will be stored. No HIPAA identifiers will be stored.
- U01 Human Placenta Project (HPP) funding under the aegis of NICHD is an organized collaborative effort. Through this mechanism, we may carry out biochemical, genomics and proteomics research but by virtue of our data being de-identified none of the findings can be traced back to a specific participating individual. We do not intend to use these samples for stem cell research or for research activities that may be considered societally unacceptable from human protection perspective.
- Specimens may be used solely by UW researcher collaborating with other U01 HPP centers or with other research institutions.

- Data shared with outside collaborators will be anonymized.
- Data may be stored indefinitely
- Study subjects may not withdraw biosamples once they have been processed.

Data Management

The PI and co-investigators will oversee the management of the study data.

This study will utilize the clinical research management software, Online Collaborative Research Environment (OnCore) and Research Electronic Data Capture (REDCap), both adopted and supported by the School of Medicine and Public Health (SMPH) and available to all researchers conducting clinical research studies. Both instances of the software that will be utilized for this study are supported and managed by the UW Institute for Clinical and Translational Research (ICTR).

Both software systems are sophisticated, web-based data management system that: a) ensures secure, easy data entry at multiple sites; b) integrates multiple data sources such as individual studies and patient registries; c) provides controlled, secure access to sensitive data using role-based access control; d) provides workflow automation; and e) allows export and reporting of data for Data and Safety Monitoring Boards and biostatisticians.

The ICTR OnCore software provides protocol and subject management functions (e.g. subject scheduling; screening, data organization), maintains updated forms, addresses budget development, billing, and fiscal management, generates summary reports, and provides essential links with other research administration and electronic medical records systems. ICTR OnCore eases the burden of the individual researcher and unifies protocol management within research programs and including researchers at multiple sites, enhancing protocol integrity and regulatory compliance efforts.

The data entered into and managed in the ICTR OnCore system is exported, then imported into ICTR REDCap and combined with MRI and U/S data, allowing the ICTR REDCap system to act as the final data repository. The REDCap data is available to the investigator and statistician(s) for reporting and analysis.

All personnel involved in the study will have undergone requisite human subjects, Good Clinical Practice (GCP) and HIPAA training, in addition to study specific data entry and management training. The MR imaging laboratory will collect, manage and store the study MRI data. The MR imaging laboratory is located within the Departments of Medical Physics and Radiology, both of which are part of the Affiliated Covered Entity (ACE).

Primary Source Documents

The investigators must maintain primary source documents supporting significant data for each subject in the subject's medical notes. These documents, which are considered 'source data', will include documentation of:

- Demographic information
- Evidence supporting the diagnosis/condition for the subject is being studied

- General information supporting the subject's consent to participate in the study
- General history and physical findings
- Hospitalization or Emergency Room records (if applicable)
- Each study visit by date, including any relevant findings/notes by the investigator(s), occurrence (or lack) of adverse events, and the date study intervention commenced and completed
- Any additional visit during the study
- Any relevant telephone conversations with the subject regarding the study or possible adverse experiences
- Original, signed informed consent forms for study participation.

The investigator must also retain all subject specific reports or tests/procedures performed as a requirement of the study (e.g., laboratory results). This documentation, together with the subject's and newborn's hospital/site medical records, is the subject's 'source data' for the study.

Case Report Forms

Case Report Forms (CRFs) will be developed and maintained with the assistance of the ICTR Study Monitoring Services, the ICTR Data Monitoring Committee and the OnCore Support specialist(s) for recording relevant data for each subject. It is the investigator's responsibility to ensure that these are properly, legibly and fully completed and signed where appropriate. The CRFs are used to record study data and are an integral part of the study and subsequent reports.

Data/Record Retention

Records will be retained for a minimum of 7 years after study completion, per UW Madison policy and IRB guidance: <https://kb.wisc.edu/sbsedirbs/page.php?id=42378>.

FDA Considerations

Ferumoxytol

Principal Investigator has an approved IND application and IRB approval to use ferumoxytol in the main arm of our placenta imaging study. We will apply the same process for this sub-project and have submitted an addendum to our IND to expand the scope of Ferumoxytol use in this sub-project for placental imaging.

MRI

All hardware used to obtain MR images is FDA approved and will be used in accordance with the conditions approved by FDA. The investigational software being used in image acquisition is designed to stay within the current guidelines for MRI safety, established by the FDA. In addition, the investigational software does not meet the definition of a Significant Risk Device as outlined by the FDA under 21 CFR 812.3 as being:

1. Intended as an implant and presents a potential for serious risk to the health, safety, or welfare of a subject;

2. Purported or represented to be for use supporting or sustaining human life and presents a potential for serious risk to the health, safety or welfare of a subject;
3. For a use of substantial importance in diagnosing, curing, mitigating, or treating disease, or otherwise preventing impairment of human health and presents a potential for serious risk to the health, safety or welfare of a subject; or
4. Otherwise presents a potential for serious risk to the health, safety, or welfare of a subject.

The scan protocol will include the following sequences
Localizer scans – FDA approved, clinical sequence

Specific Aim 1: MRI Flow

- 2D Phase Contrast MRI (Flow Imaging) = FDA approved, clinical sequence

Specific Aim 2: MR Perfusion and Oxygenation

- Oxygenation (BOLD MRI) – multi TE gradient echo sequence = FDA approved sequence

Specific Aim 3: MRI Ferumoxytol DCE perfusion data (not investigational sequences) and localization of immune cells.

DATA AND SAFETY MONITORING

Data and Safety Monitoring Plan

We use the UW ICTR Data Monitoring Committee for the purpose of oversight over this study. We have accounted for the fees for the Data Safety Monitoring. The clinical investigator, [name], the PI, [name] and the co-investigator [name], respectively, are responsible for reporting any adverse responses or events that occur. These are reported as per requirement to UW IRB, and to the Data Monitoring Committee. We take advice from the IRB committee and Data Monitoring Committee for appropriate modifications of our procedures in order to avoid such events.

For subjects receiving the ferumoxytol infusion, the PI and study team will monitor any potential impact on the subject and the fetus. The subject will be closely monitored by triage clinical staff during the infusion of ferumoxytol in the triage unit, including the collection of vital signs. With any signs of reactions, the infusion will be stopped. The study coordinator will report any events of this nature, including adverse events and unanticipated problems, to the PI and the DSMB within one business day.

In the weeks following infusion, the PI will discuss the imaging results with the subject and the clinician providing direct care to the subject. Any adverse events will be documented, entered into the subjects study file and reported to the DSMB. After delivery, pregnancy outcome and any potential impact on the fetus will be documented and reviewed with the PI and subject clinician and DSMB. Development of pre-

eaclampsia and FGR will not be considered, but will be reported, as an adverse event secondary to ferumoxytol infusion.

Data Monitoring Committee (DMC)

UW-ICTR has established a Data Monitoring Committee (DMC) to provide a key resource for UW-Madison investigators conducting clinical research. We plan to utilize the UW-ICTR DMC services to ensure appropriate measures are in place to promote subject safety, research integrity and compliance with federal regulations and local policies for individual clinical research protocols. These protocols are deemed in need of DMC review by the PI, the funding agency, the local Scientific Review Committee, or the local IRB, and for which no DMC exists. For these studies, the UW ICTR DMC is the primary data and safety advisory group for the Principal Investigator.

The DMC is supported in its mission of safety and compliance by experienced ICTR staff to provide administrative assistance, experienced members representing a diversity of backgrounds, skills and knowledge, and the use of the ICTR OnCore clinical research management system which allows more efficient tracking of protocols and protocol subjects. In providing oversight for the conduct of this study, the ICTR DMC meets annually during the length of study. Additional meetings are scheduled as determined by the DMC or as requested by the PI. The DMC members review protocol-specific reports created by statisticians that serve a non-voting member role on the DMC using data pulled from the ICTR OnCore clinical research management system. These standard reports include an overview of study objectives, a review of actual and projected accrual rates, an evaluation of patient demographics for balance of randomization, and a summary of the number and seriousness of adverse events.

An interim analysis of study results may be performed and source documents may be reviewed to allow the DMC to independently judge whether the overall integrity and conduct of the protocol remain acceptable based on data provided and reported by the Principal Investigator. The DMC will make recommendations to the Principal Investigator that could include actions of continuation, modification, suspension, or termination.

ICTR Study Monitoring Service (SMS)

While many institutions involved in clinical research conduct various types of quality assurance reviews and audits, UW ICTR is one of the few institutions to offer independent Study Monitoring Services, a robust academic equivalent to the Industry Contract Research Organization (CRO) standards for ongoing study monitoring.

The Study Monitor Services have been contracted for in the placental study, and include the conduct and follow-up of monitoring visits throughout the life cycle of the study (e.g., Study Initiation Visit, Interim Monitoring Visits, and Close-Out Visit). Study monitoring visits occur off-site (remotely) and/or on-site at a frequency necessitated by the protocol risk and complexity. For this study, UW ICTR SMS personnel will conduct a Study Initiation Visit (SIV) with the University of Wisconsin's research personnel in person after IRB approval was confirmed and before enrollment of any subjects into the study.

The SIV will include a detailed review of the protocol, good clinical practice guidelines, and data management expectations of the research team at the study site and SMS personnel.

Following the Study Initiation Visit (SIV), SMS personnel will routinely conduct ongoing Interim Monitoring Visit (IMVs) for all data collection sites, either on-site, remotely or a combination of both, following enrollment of the first subject(s) and throughout the duration of the study. During the IMVs, the monitor will review study materials, including but not limited to: regulatory files, consent forms, case report forms, and drug accountability logs. SMS personnel will review compare the electronic data to that of the primary source documents and case report forms (described above). UW ICTR SMS personnel will conduct a Close-Out Visit (COV) upon completion of the study at the study site.

Monitoring consists of full or partial review of study records, depending on the risk level and observed compliance. As such, during their monitoring activities, UW ICTR SMS personnel plan to review all (100%) of the study-related subject records for 10% of the enrolled subjects. SMS personnel could increase the percentage of study or subject records to be reviewed if warranted by the ongoing monitoring findings. The study monitor(s) work with the ICTR DMC statistician to conduct periodic central data reviews, with follow-up conducted by the study monitors for any data discrepancies identified.

